4.2 Multiple comparisons

We will complete multiplicity adjustment as noted in the CSP Section 8.8. The primary and top secondary outcomes will be tested sequentially, and thus, no multiplicity adjustment is necessary

4.3 Right Censoring

In this study we expect missing outcome data to be infrequent and every effort will be made to collect all information regarding the primary outcomes prior to study termination, even in those who have discontinued the study treatment.

For all analyses covered by this SAP, the observation time for participants who have not had an event in the analysis of a specific outcome will be right censored at the date of last contact where any elements of the outcome could be assessed unless otherwise specified. Same algorithm will be followed for inclusion of events in the analyses.

Note that for the analysis of the components of the primary composite outcome, participant exposure will be censored at the date of the occurrence of the component outcome of interest.

Note that for outcomes not including CV death, all deaths are censoring events.

In safety time-to-event analyses in the Safety population, participants who have not had the event in question will be censored following same rules as detailed for the ITT population.

4.4 Handling of Missing Data

4.4.1 Outcome Data/Dates

The primary analysis will rely on a multiple imputation model, with Markov chain Monte Carlo algorithm based on the totality of observed data. One exception to this rule will be that

individuals unable to perform the 6MWT test at 6 months i.e. those who did not perform a 6MWT or died prior to 180 days will have their value imputed as the worst possible 6MWT distance which is 0 meters. Any missing death dates will be imputed using date imputation rules in this section. A baseline 6MWT distance is needed to be able to calculate change from baseline 6MWT, hence, any missing baseline 6MWT distance will be imputed as overall mean to allow full ITT population to be included in primary analyses.

The SAS PROC MI procedure will be used for multiple imputations on the 6 month 6MWT distance, with 20 imputations. To ensure consistency in the imputed data for future possible validations, a seed number will be fixed to 1000. Baseline 6MWT, treatment and region will be included as covariates in the imputation model. We will include all observed data in the imputation model with the exception of participants unable to perform 6MWT at 6 months who will have their 6MWT distance included as 0 meters before performing multiple imputation. Imputed data set(s) will include an index variable to identify the number of imputed data. The results across the imputed datasets will be combined using Rubin's rule ([Rubin 1987](#)) to obtain one set of results for the primary analysis. These same missing data handling rules will be used for the Win-Ratio analyses. Basic statistics on the overall original data (incomplete data) and the data following imputation will be provided in the Clinical Study Report (CSR).

For secondary efficacy endpoints, missing data relating to the indicator for the confirmed composite CV outcome and/or its components will not be imputed. Any partial or completely missing date for a confirmed composite CV outcome at the time of database lock will be imputed as follows:

- If the day is missing, 15th of the month, or the randomization date (if participant randomized after 15th of the same month and same year) will be used, making sure the imputed date is not post date last known alive on end of study form;
- If the month is missing, June, or the randomization month (if participant randomized after June and year of the event is same as randomization year) will be used, making sure the imputed date is not post date last known alive on end of study form;
- If the complete date is missing, the midpoint between randomization and the date of last known event-free visit will be used with the exception of death date.
- If the death date is completely missing, it will be imputed to be the date after last contact date.

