- i. All participants randomized will be dosed every 6 months. Participants randomized to the FCM arm will be dosed as indicated based on blood counts (i.e. Hgb <13.5 g/dL [females] or <15.0 g/dL [males])) and iron studies (i.e. serum ferritin <100 ng/mL or 100 to 300 ng/mL with TSAT <20%). Participants not meeting pre-specified laboratory criteria for blood counts and iron studies and all participants randomized to the placebo arm will be administered IV placebo infusion at each visit. The second of the 2 dosing visits should occur at Day 7±2 after the first dose.
- j. Prior to randomization
- k. Only for participants at select sites performing additional chemistry labs (1,25 (OH)₂ Vitamin D, 25 (OH) Vitamin D and PTH) (sub-study).
- l. May be performed via telephone or in person.
- m. Performed at Day 180 and Day 360 visits only.
- n. To be performed by unblinded site personnel. All other procedures must be performed by personnel blinded to the treatment assignment
- p. Hemoglobin only

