In order to maintain an overall alpha of 0.01 and account for interim analysis we will use a two-sided alpha of 0.0099 for the final analysis of the primary endpoint.

At the request of the FDA, the overall alpha for the top secondary endpoint was changed from 0.05 to 0.04. In order to maintain an overall alpha of 0.04 and account for interim analysis we will use a two-sided alpha of 0.0399 for the final analysis of the top secondary endpoint.

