7 DATA SAFETY MONITORING BOARD AND INTERIM ANALYSES

7.1 Interim Analyses

The below text regarding interim analyses is as is written in the CSP 1VIT15043, version 3.0, 11 January 2021. The overall alpha levels to be used for primary and top secondary analyses are described in section 1.4.

A Data and Safety Monitoring Board (DSMB) Committee will review safety data, including a tally of the composite outcome events at least every 6 months. The DSMB can recommend stopping the study for safety concern at any point. In addition, one interim analysis is planned to determine if an early stopping for an overwhelming efficacy should be recommended or if an increase in sample size is warranted. The details as identified in Section 8.10 of the protocol are that this analysis will be conducted after 2250 (75%) participants have been randomized. Significance level will be set at 0.0001 for this analysis, resulting in an adjusted significance level for the final analysis of 0.0099 for the primary endpoint and 0.0499 for the first secondary endpoint, preserving the overall significance at 0.01 and 0.05, respectively. Conditional power will be estimated based on data accrued to date and presented to the DSMB.

The DSMB may recommend that the study continues as planned, discontinue the study, or that the trial be continued with recommended changes to the protocol.

The Executive Steering Committee will determine if an increase in sample size is warranted in order that at least 771 participants will experience an event of CV death or hospitalization for heart failure.

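### Twenty imputations leave avoidable Monte Carlo error in the primary p-value near 0.0099; separately, the named imputation covariates leave out the collected 12-month walk

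*Combined protocol and SAP*

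**What the plan says.** SAP v1.3 section 4.4.1 makes multiple imputation the primary method for missing 6-month walks. It specifies "The SAS PROC MI procedure will be used for multiple imputations on the 6 month 6MWT distance, with 20 imputations", says that "a seed number will be fixed to 1000", and pools by Rubin's rule. On the model it says "Baseline 6MWT, treatment and region will be included as covariates in the imputation model". The same section opens by describing the method as one "with Markov chain Monte Carlo algorithm based on the totality of observed data" and later says that all observed data go into the model, apart from an exception worded in terms of participants. Participants unable to walk at 6 months are set to 0 m before imputation.

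Protocol version 3, section 3.3, footnote m, says of the walk test: "Performed at Day 180 and Day 360 visits only". A 12-month walk is therefore collected, and its change from baseline is a secondary endpoint (SAP section 5.5).

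On the threshold, SAP section 1.4 says "we will use a two-sided alpha of 0.0099 for the final analysis of the primary endpoint". For the interim look, section 7.1 says "Significance level will be set at 0.0001 for this analysis".

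**The concern.** A pooled p-value from a finite number of imputations carries simulation error of its own. The SAP accounts for an interim look by moving the final threshold by 0.0001. Under the assumptions below, the simulation error in p from 20 imputations is many times that adjustment when p is near the threshold. Which side of 0.0099 a borderline result falls on would then depend partly on what seed 1000 happens to draw.

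The predictor list is a different matter. Someone who missed Month 6 but walked at Month 12 has a relevant measurement in the database, and the three named covariates do not use it. Some information is lost, and the missing-at-random assumption is conditioned on less than the trial collected.

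**Working it through.** **Threshold.** 0.01 - 0.0001 = 0.0099, as stated in SAP section 1.4. The two-sided critical value is z = 2.579.

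**Inputs from the SAP.** N = 3014, 1507 per arm; the event rates and walk change (means 0 and 18 m, SD 90 m) in Table 1.4.1; 15% of 6-month walks missing, which combines unable and lost to follow-up; m = 20 imputations.

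**Assumed inputs, not in the documents.** Share of walks multiply imputed, 5-15% (the 0 m rule removes some of the planned 15%); baseline walk mean 270 m, SD 100 m; no effect of region.

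**Fraction of missing information (FMI).** I simulated the three-tier ranking, imputed the walk by normal regression on baseline and arm, and pooled the win probability by Rubin's rule. FMI was about 0.04, 0.06 and 0.095 at 5%, 10% and 15% imputed.

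**Seed noise.** The SD of the pooled z over seeds is about sqrt(FMI/m). At 10% imputed and m = 20 it is sqrt(0.06/20) = 0.055. The 95% range of p is the two-sided p at 2.579 ± 1.96 × SD:

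| Imputed | FMI | SD of z, m = 20 | p range, m = 20 | p range, m = 200 |
|---|---|---|---|---|
| 5% | 0.04 | 0.045 | 0.0077-0.0127 | 0.0091-0.0107 |
| 10% | 0.06 | 0.055 | 0.0072-0.0134 | 0.0090-0.0109 |
| 15% | 0.095 | 0.069 | 0.0066-0.0145 | 0.0087-0.0112 |

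Varying the seed 2000 times by simulation at 15% imputed gave 0.0064-0.0159 at m = 20, slightly wider than the formula, and 0.0090-0.0108 at m = 500. The SD of p at m = 20 was 0.0013 (5% imputed) to 0.0024 (15% imputed), which is 13 to 24 times 0.0001.

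**How often the decision would differ.** The chance that m = 20 and unlimited imputations disagree is about SD × sqrt(2/π) × φ(z for the power). With SD 0.06 and the stated 90% power, this is 0.06 × 0.798 × 0.176 = 0.8%. At 97-99% power, which the simulation gave when missing walks were multiply imputed under the planning rates, it is about 0.1-0.3%.

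**12-month walk: precision.** With within-imputation variance held equal, the standard error shrinks by the factor sqrt((1 - FMI without)/(1 - FMI with)).
- If 60% of those missing Month 6 have a Month 12 walk and the residual correlation is 0.6-0.75 (both assumed), FMI falls from 0.077 to 0.059, or from 0.046 to 0.030. Then sqrt(0.923/0.941) = 0.990 and sqrt(0.954/0.970) = 0.992, a gain of about 1%.
- A more favourable case (15% imputed; assumed correlation of the 12-month walk with the 6-month change 0.5 or 0.7) takes FMI from 0.095 to 0.074 or 0.045, a gain of 1.1% or 2.7%.

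**12-month walk: seed noise.** In that second case at m = 20, the simulated p range moves from 0.0064-0.0159 to 0.0067-0.0148 (correlation 0.5) or 0.0074-0.0134 (0.7). Raising m to 100 without the extra walk gives 0.0082-0.0120.

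**Heart-failure events.** Adding a hospitalization indicator (assumed 30-100 m worse walk; 15% or 35% missing among those hospitalized) moved the mean pooled z by about 0.06 at most. Under SAP section 5.1 the walk is compared only after deaths and hospitalization counts are tied, so those participants are already ranked lower.

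**The case against.** - **The seed is fixed in advance.** A reader might infer that a favourable seed could be chosen. The documents do not support that: section 4.4.1 sets it at 1000. This answers selection, but the single draw remains arbitrary.
- **The decision is rarely affected.** At under 1% under the planning assumptions, this is correct. The remedy is also close to free.
- **The model may be wider than three covariates.** A reader might infer that the SAP uses only those three and deliberately ignores the rest. It never says so, and its references to the totality of observed data could be read more widely. The narrow model is the likelier reading, because the stated exception concerns participants and no other predictor is named. What can be asserted is that the list is not stated as closed.
- **The short list does not cause the seed dependence.** A reader might link the two. The figures above show that the number of imputations is what matters.
- **The 0 m rule may leave few walks to impute.** Read literally, its definition could cover anyone who did not walk at Month 6. But section 5.3.1.7 sets every missing walk to 0 m as a separate supportive analysis, so the primary analysis must leave some to imputation. A smaller imputed share reduces the noise without removing it (5% row).
- **Sensitivity analyses already exist.** Sections 5.3.1.2, 5.3.1.7 and 5.3.1.8 test the missing walks harder than extra predictors would. None of them varies the number of imputations or the seed.

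**Conclusion.** The point about the number of imputations stands as an inexpensive improvement to the primary analysis. At m = 20, an underlying p of 0.0099 would be reported anywhere from about 0.007 to 0.014 at 10-15% imputed, or 0.008 to 0.013 at 5%. With 200 imputations the range is about 0.009 to 0.011. Results well away from 0.0099 are unaffected.

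The omission of the 12-month walk is a smaller, separate point, worth about 1% of the standard error. That figure depends on correlations and availability that the documents do not give. A reader might go further and infer that leaving out heart-failure events distorts the primary test. Under the planning rates the calculation does not support that. The effects of NYHA class, NT-proBNP and age were not quantified.

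**What to change.** In SAP section 4.4.1:

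1. Raise the number of imputations from 20 to at least 200 and keep the seed at 1000.
2. Add the 12-month walk distance as an auxiliary variable for participants whose 6-month walk is multiply imputed rather than set to 0 m, and state how a 12-month walk that was not performed enters the model.
3. State the variable list as closed, and align the sentences about the totality of observed data with it.

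Heart-failure hospitalizations, NYHA class, NT-proBNP and age are optional additions. The win ratio already follows the same missing-data rules, so it needs no separate change. The cost is a few sentences, settled before unblinding, and computing time.

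### SAP v1.3 Section 4.4.1 dates a fully undated non-fatal event inside time known to be event-free, and caps a partly dated death at the date last known alive

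*Combined protocol and SAP*

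**What the plan says.** SAP v1.3 Section 4.4.1 gives rules for confirmed cardiovascular events whose date is incomplete at database lock. It introduces them for the secondary efficacy endpoints.

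- Day missing: "If the day is missing, 15th of the month, or the randomization date", the second option applying when randomization fell later in that same month.
- Month missing: "If the month is missing, June, or the randomization month (if participant randomized after June and year of the event is same as randomization year").
- Both partial-date rules carry a cap: "making sure the imputed date is not post date last known alive on end of study form".
- Whole date missing: "the midpoint between randomization and the date of last known event-free visit will be used", except for deaths.
- Whole death date missing: "If the death date is completely missing, it will be imputed to be the date after last contact date".

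Higher up, the same section sends missing death dates in the primary analysis to these rules. Section 4.3 censors participants without an event at the last contact that allowed some part of the outcome to be judged, leaves room for exceptions stated elsewhere, and adds: "Same algorithm will be followed for inclusion of events in the analyses". Section 4.1 ties the date of last contact to the last visit performed. It mentions the date last known alive as an end-of-study-form item for participants who withdrew consent.

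**The concern.** An imputed date should fall in the interval where the event could have occurred. For a non-fatal first event, that interval opens at the last visit known to be event-free. For a death, it opens at the last date known alive. Section 4.4.1 uses the first of these as the far end of its midpoint and the second as a ceiling, so in both places a lower limit is treated as an upper one.

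The sponsor has already moved away from the midpoint rule for deaths. In SAP v1.0 Section 4.5.1 it covered every event, and partial dates were capped at the end-of-study date. Version 1.3 exempts deaths from the midpoint but leaves it in place for heart failure hospitalization, the other component of the top secondary outcome. It also replaces the end-of-study cap in the event-date rules with the date last known alive.

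At stake are event times in the Cox analyses of the secondary outcomes and, through the death dates, survival time in the top tier of the primary hierarchy (SAP Section 5.1). Poorly documented deaths are foreseen. Protocol Sections 4.4 and 4.6 provide for vital-status searches after contact is lost. Protocol Section 10.2.1.8 counts deaths of undetermined cause as cardiovascular.

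**Working it through.** The plan states no figure to reproduce, so the check applies each rule to simple timelines. Randomization is day 0 (the SAP's +1 day convention is ignored) and L is the day of the last event-free visit. The next contact is taken as L + 90, an assumption based on the 3-month contact interval in protocol Section 3.1.

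**1. Fully missing non-fatal date**

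SAP date = (0 + L)/2 = L/2. The true date T is later than L. For every L > 0, L/2 < L < T, so the SAP date always lies in event-free time. The error T − L/2 exceeds L/2.

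The interval midpoint is (L + L + 90)/2 = L + 45.

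| L (days) | SAP date L/2 | Interval midpoint L + 45 | Difference (days) |
|---|---|---|---|
| 90 | 45 | 135 | 90 |
| 180 | 90 | 225 | 135 |
| 360 | 180 | 405 | 225 |
| 720 | 360 | 765 | 405 |

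In months, with the last event-free visit at 18 and the report at 21, the SAP date is (0 + 18)/2 = 9 and the interval midpoint is (18 + 21)/2 = 19.5. The difference is 10.5 months. The error grows with follow-up, because it depends on L and not on the width of the interval in which the event occurred.

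**2. Partly missing non-fatal date**

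The only lower limit is randomization. Take an event-free visit on 24 September.

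- Event known only as September of that year: dated 15 September, 24 − 15 = 9 days before the event-free visit.
- Event known only by year: dated 15 June if the month and day rules are chained, 15 + 31 + 31 + 24 = 101 days before the visit.

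These conflicts arise only when there is a later event-free visit in the same month or year. The last-known-alive cap causes no harm here, since a hospitalization cannot follow the last date alive.

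**3. Partly missing death date**

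Take a participant last known alive on 8 September.

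- Death known only as September: the day rule gives 15 September, which is possible. The cap pulls it back 7 days to 8 September, when the participant was recorded alive.
- Death known only by year: 15 June if the rules are chained, 15 + 31 + 31 + 8 = 85 days before a date on which the participant was alive. Here the cap does not bind; the missing lower bound is the problem.

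**4. Fully missing death date**

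With last contact on 24 September, the imputed death is 25 September, one day past the date that closes the window if Section 4.3 is read without its exception clause.

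**5. How many events**

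The documents give no count of missing dates. If 1 to 20 events were affected (an assumption), that is 1/771 = 0.1% to 20/771 = 2.6% of the planned 771.

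**The case against.** The strongest reply is that the midpoint rule will have almost nothing to act on. A confirmed heart failure hospitalization requires a stay of at least 24 hours or, failing times, a change of calendar date (protocol Section 10.2.2.1). An adjudicated admission with no day, month or year is hard to imagine. The rules also apply without regard to treatment arm, and Section 4.3 expects missing outcome data to be infrequent. All of this stands and limits the impact. It does not make the midpoint a possible date.

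The cap sits in a list that covers fatal and non-fatal events together, and for hospitalizations it is right. That stands too, so the objection to the cap is confined to deaths. It may bind rarely, since Section 4.1 mentions the date last known alive only for withdrawn-consent participants and the form itself is not available.

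Three stronger readings are tempting, and the documents do not support them.

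- A reader might infer that the midpoint rule moves hospitalizations from after month 12 into the first-year count of the primary endpoint. The rule is written for the secondary endpoints; only missing death dates are expressly carried to the primary analysis, and a fully missing death date is exempt from the midpoint. The secondary outcomes are times to first event with no one-year cut.
- A reader might infer that a death dated one day after last contact is dropped under Section 4.3. That section defers to rules specified elsewhere, and Section 4.4.1 is a specific rule for exactly this death. Reading it so that it always excludes the death it dates would be perverse. Inclusion is the natural construction, although the text does not say so.
- A reader might infer that every imputed date is much too early. Only the midpoint rule always gives a date that is too early by at least half the event-free period. The cap costs 7 days in the example, and the mid-month and June defaults can fall on either side of the true date.

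**Conclusion.** The midpoint rule for a fully undated non-fatal event is wrong as written, and no other section corrects it. Whenever there is an event-free visit after randomization, the imputed date is impossible and more than half the event-free period too early. This assumes that a first event is being dated, so that an event-free visit implies no earlier event. It concerns the secondary time-to-event endpoints.

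The last-known-alive cap is wrong for partly dated deaths only. It can place a death on or before a date on which the participant was recorded alive, and through the death-date rules this reaches the primary analysis. For non-fatal events the cap is correct.

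The treatment of a fully undated death is a matter for clarification, not an error.

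With few missing dates expected, the effect on the hazard ratio is probably small; the assumed 0.1% to 2.6% of events shows the scale and is not an estimate. This is a drafting correction worth making because it is cheap, not because it threatens the conclusions.

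**What to change.** Amend SAP Section 4.4.1 as follows.

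- Fully missing date of a non-fatal event: use the midpoint between the last event-free visit and the first contact at which the event was known.
- Partly missing dates: keep the mid-month and June defaults, but do not let the imputed date fall before the last known event-free date (non-fatal event) or the last known alive date (death), while staying within the month or year that is known.
- Keep the last-known-alive upper cap for non-fatal events only.

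For clarity, add one sentence to Section 4.3 or 4.4.1 stating that a death imputed to the day after last contact counts as an event.

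The cost is a few lines of SAP text and a small programming change before unblinding. The visit and contact dates needed come from the existing 3-month schedule, so no new data are required.

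The number of imputed dates by rule and arm should be reported, so that a reader can see how little, or how much, depends on them.
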